7.5 Exclusion criteria

- Active electrical implant/device in any region of the body, including pacemaker or internal defibrillator
- Permanent implant in the treated area such as metal plates, screws or silicon, metal piercing or other.

I N M O D E

Safety and Efficacy of Trim II for Non-invasive Lipolysis and Circumference Reduction of Abdomen.

Protocol No: DO609924A SIRB ID: 8659

Rev. Date: Jun 3 2022

- Current or history of skin cancer, or current condition of any other type of cancer, or pre-malignant moles.
- Severe concurrent conditions, such as cardiac disorders, sensory disturbances, epilepsy, uncontrolled hypertension, and liver or kidney diseases.
- History of skin disorders, keloids, abnormal wound healing, as well as very dry and fragile skin.
- History of bleeding coagulopathies or use of anticoagulants except for low-dose aspirin.
- Patients with history of diseases stimulated by heat, such as recurrent Herpes Simplex in the treatment area, may be treated only following a prophylactic regimen.
- Impaired immune system due to immunosuppressive diseases such as AIDS and HIV or use of immunosuppressive medications.
- Pregnancy and nursing.
- Poorly controlled endocrine disorders, such as Diabetes, or thyroid dysfunction and hormonal virilization.
- Isotretinoin (Accutane) within last 6 months.
- Any active condition in the treatment area, such as sores, Psoriasis, eczema, and rash, open lacerations, abrasions or lesions, infection in the area to be treated.
- Any surgical procedure in the treatment area within the last 12 months or before complete healing.
- Having received treatment with light, laser, RF, or other devices in the treated area within 2-3 weeks for non-ablative procedures, and 6-12 weeks for ablative fractional laser resurfacing (according to treatment severity) prior to treatment, except special recommendations.
- Use of non-steroidal anti-inflammatory drugs (NSAIDS, e.g., ibuprofen-containing agents) one week before and after each treatment session, as per the practitioner's discretion.
- As per the practitioner's discretion, refrain from treating any condition which might make it unsafe for the patient
- Participated in another investigational drug or device study or have completed the follow-up phase for any previous study less than 30 days prior to the first evaluation in this study.

8. Study Procedures

Each subject will undergo at least 5 study visits including: screening, 3 treatments and 2 follow-up visits. Duration of each treatment visit is approximately 2 hours.

The Time and Events Schedule is provided in Appendix 1.0.

8.1 Visit 1: Screening, baseline and 1st treatment

Screening visit will be performed in order to determine subject eligibility and to collect all required demographic and baseline clinical information. Study procedures and available treatment options, including RF and EMS technologies will be described in detail to the subject. Subject will be assured that the decision regarding participation in the study is strictly voluntary and that they are free to change their mind at any stage.

	Safety and Efficacy of Trim II for Non-invasive Lipolysis and Circumference Reduction of Abdomen.	
	Protocol No: DO609924A SIRB ID: 8659	Rev. Date: Jun 3 2022

The subject will review the informed consent form and the study will be explained to the subject including risks, potential benefits, procedures, visit requirements, and other alternative treatment options. If the subject qualifies and wishes to participate, he/she will complete the ICF with a signature and date. The original will be retained with subject's records and a copy will be provided to the subject. Subjects will then be screened for study eligibility according to inclusion and exclusion criteria.

The following Demographic and Baseline Measurements will be performed:

Screening:

- Demographic data including gender, age, race, skin type (Fitzpatrick scale).
- ICF - Prior to any study procedures, informed consent will be obtained. When the subject fully understands the possible benefits and risks of the study, the subject will be asked to sign and date the informed consent form (ICF). The subject will be given a copy of the signed ICF.
- Subject ID - subjects will be assigned a study subject ID number.
- Medical History - A medical history will be obtained to determine if the subject meets the study criteria, including a list of all prescribed and over the counter medications taken within the previous 6 months will be recorded.
- Pregnancy Screen - Subjects who are capable of becoming pregnant will undergo a urine pregnancy test. This will be repeated prior to all treatments, and at the end of the study (last FU visit, 3-month FU).
- Weight and height (BMI calculation)
- Pregnancy Urine Test prior to the treatment

Baseline:

- Baseline abdominal fat thickness measured by ultrasound. Appendix 2.0
- Baseline photographs of treatment area - Photography – Baseline photographs will be obtained using a consistent camera and subject placement settings with a digital imaging system. Appendix 3.0
- Baseline circumference tape measurement. Appendix 4.0
- Baseline caliper measurement
- Baseline histologies (8 subjects – at selected sites).

Treatment:

- 1st abdominal treatment will be done using the TRIM II hands-free applicators belt according to IFU
- Subject Comfort Assessment
- * Treatment may occur on the same day of screening or within 3 weeks following screening.
- If the Screening and Treatment procedures are not conducted on the same day, the urine pregnancy test will be repeated on the first treatment day.

Treatment procedure:

- Treatment will be conducted according to instructions in the operator manual and company guidelines.

I N M O D E

Safety and Efficacy of Trim II for Non-invasive Lipolysis and Circumference Reduction of Abdomen.

Protocol No: DO609924A SIRB ID: 8659

Rev. Date: Jun 3 2022

[Redacted text block]

After treatment:

- Observation, assessment and recording of adverse events will be conducted.
- Subject will complete Therapy Comfort Questionnaire

8.2 Visits 2-3: 2nd , 3rd treatments , every 2 weeks following previous visit

- Pregnancy Urine Test prior to the treatment
- Weight and height (BMI calculation)
- Circumference tape measurement
- Caliper measurement
- Abdominal treatment will be done using the TRIM II hands-free applicators belt according to IFU

	Safety and Efficacy of Trim II for Non-invasive Lipolysis and Circumference Reduction of Abdomen.	
	Protocol No: DO609924A SIRB ID: 8659	Rev. Date: Jun 3 2022

- Therapy Comfort Questionnaire

8.3 Visit 4: Follow-up visit – 1 month following last treatment

- Treatment area will be photographed
- Weight and height (BMI calculation)
- Circumference tape measurement
- Caliper measurement

8.4 Visit 5: Follow-up visit – 3 months following last treatment

- Treatment area will be photographed
- Pregnancy Urine Test prior to the treatment
- Weight and height (BMI calculation)
- Circumference tape measurement
- Caliper measurement
- Abdominal fat thickness measured by ultrasound
- Histologies (8 subjects)
- Subject's satisfaction

After each treatment and at all visits, any adverse events will be recorded.

	Safety and Efficacy of Trim II for Non-invasive Lipolysis and Circumference Reduction of Abdomen.	
	Protocol No: DO609924A SIRB ID: 8659	Rev. Date: Jun 3 2022

8.5 Table 1 – Clinical Evaluation Measurements and Tools

Measurement	When to conduct	Method
Height	Baseline, Prior to every treatment and at follow-up's visits	Scale
Weight		Scale
BMI		Calculation
Circumference	Baseline, Prior to every treatment and at follow-up's visits	Tape Measurement (Appendix 4.0)
Caliper	Baseline, Prior to every treatment and at follow-up's visits	Caliper
Photographs	Baseline, and at follow-up's visits	Standardized digital photographs (Appendix 3.0)
Urine pregnancy test	Baseline, Prior to every treatment and at last follow-up visit (3 months)	Urine pregnancy test
Ultrasound imaging	Baseline and last follow-up visit	Abdominal US (Appendix 4.0)
Histology (8 subjects)	Baseline and last follow-up visit	Biopsies taken from treatment areas
Therapy Comfort	After every treatment	Therapy Comfort Questionnaire (Appendix 5)
Immediate response assessment	Immediately after each treatment	Complete in CRF
Subject satisfaction	Last follow-up visit	Subject Satisfaction Questionnaire (Appendix 5)
Safety- AE	During treatment and throughout study.	Examination of skin in the treated area, interview subjects, Adverse Events form, Occurrence and Severity Ratings, as well as relation to treatment, action taken and outcome

9. Adverse Events Reporting

9.1 Definitions

Adverse Event:

An adverse event (AE) is any adverse change in health or side effect that occurs in a study participant during their participation in the study.

Serious Adverse Event (SAE):

A serious adverse event (SAE) is any adverse event that:

- Led to death
- Led to a serious deterioration in the health of the subject that resulted in a life-threatening illness or injury
- Resulted in a permanent impairment of a body structure or a body function
- Required in-subject hospitalization or prolongation of existing hospitalization

	Safety and Efficacy of Trim II for Non-invasive Lipolysis and Circumference Reduction of Abdomen.	
	Protocol No: DO609924A SIRB ID: 8659	Rev. Date: Jun 3 2022

- Resulted in medical or surgical intervention to prevent permanent impairment to body structure or a body function
- Led to fatal distress, a congenital abnormality, birth defect or death

Unanticipated Adverse Event:

An unanticipated adverse event is any serious, device-related adverse event, if that event was not previously identified in the risk analysis and Informed Consent form in nature, severity, or frequency.

AE Severity:

Adverse events are graded according to severity as follows (Table 2):

Mild	Sign or symptom, usually transient, requiring no special treatment and generally not interfering with usual activities.
Moderate	Sign or symptom, which may be ameliorated by simple therapeutic measures; yet, may interfere with usual activity.
Severe	Sign or symptom that are intense or debilitating and that interfere with usual activities. Recovery is usually aided by therapeutic measures.

Relationship to Device:

The relationship of the adverse event to the treatments or procedures is defined as follows (Table 3):

Most Probably Related:	Follows a reasonable temporal sequence from study device delivery/retrieval and cannot be reasonably explained by known characteristics of the subject's clinical data or the surgical procedure applied.
Possibly Related:	Follows a reasonable temporal sequence from study device delivery/retrieval but could have been produced by the subject's clinical state or by the surgical procedures regardless of the study device.
Probably not Related:	Temporal association is such that the study device is not likely to have had any reasonable association with the observed event.
Unrelated	No relationship to study device activation is perceived

9.2 Anticipated Adverse Events in this Clinical Evaluation

Possible Trim II adverse effects include but are not limited by:

- Pain

	Safety and Efficacy of Trim II for Non-invasive Lipolysis and Circumference Reduction of Abdomen.	
	Protocol No: DO609924A SIRB ID: 8659	Rev. Date: Jun 3 2022

- Excessive redness (erythema)
- Swelling (edema)
- Muscles spasm
- Treatment area infection
- Skin irritation and burns beneath the electrodes have been reported with the use of pain
- Skin burn
- Pigmentation change
- Scar

*Erythema and edema lasting not longer than 24h is typical skin reaction to the treatment.

*Skin irritation and burns beneath the electrodes have been reported with the use of powered muscle stimulators.

9.3 Precautions to Minimize Complications

A list of warning and precautions is provided in the Operator Manual which is provided to site personnel. Additionally, the exclusion criteria listed in this protocol further reduce the above-mentioned risks.

9.4 Investigator Records

The Investigator will report all Adverse Events which occur with each subject throughout the study and follow-up period and will record them in the CRF Adverse Events Investigation Form. The Investigator will categorize Adverse Events according to:

- Serious or non-serious
- Severity
- Anticipated or unanticipated
- Relationship to device use

9.5 Investigator Reporting of AEs

The Investigator will report all serious adverse events (SAEs) to InMode Ltd by telephone as soon as becoming aware of them. A written follow-up report will be emailed or faxed to InMode Ltd and the reviewing IRB within 24 hours and will include the following information:

1. Nature of AE
2. Statement regarding the degree to which it is considered device related, and rationale.
3. Results of any diagnostic tests that were performed.
4. Description of any treatment implemented.
5. Statement of subject's current clinical status.
6. Investigator's signature and date.

Non-serious adverse events that are unanticipated and may be device related will be reported to the InMode Ltd by telephone within 24 hours. A written follow-up written report will be emailed or faxed to InMode Ltd within 5 working days and will include the following information:

1. Nature of adverse effect.

 I N M O D E	Safety and Efficacy of Trim II for Non-invasive Lipolysis and Circumference Reduction of Abdomen.	
	Protocol No: DO609924A SIRB ID: 8659	Rev. Date: Jun 3 2022

2. Statement as to why it is considered unanticipated.
3. Statement as to the degree to which it is considered device related, and rationale.
4. Results of any diagnostic tests that were performed.
5. Description of any treatment implemented.
6. Statement of subject’s current clinical status.
7. Investigator’s signature and date.

All other Adverse Events will be reported in writing to InMode Ltd in writing within 5 working days of the Investigator becoming aware of them.

The Investigator will continue to clinically monitor the AE, with laboratory tests where appropriate, until it is resolved, stabilized or there is a return to baseline.

10. Regulatory Aspects

10.1 Institutional Review Board

The study protocol, informed Consent forms (all versions), and any specific advertising will be submitted to and approved by Sterling Institutional Review Board (IRB), at [name], Toll-Free: [contact], [contact], [contact] before the start of the study.

10.2 Informed Consent

An Informed Consent that includes all the relevant elements currently required by FDA or state regulations will be provided to each prospective study patient at screening and before enrolling into the study. The type and method of study, any potential or possible hazards, and the patient’s right to withdraw from the study at any time will be explained to the patients by the Investigator or designee. Once the Investigator is assured that an individual candidate understands the implications of participating in this study, the patient will be asked to give Consent by signing and dating in the appropriate areas of the Informed Consent form. The Investigator or Designee will also sign and date the form in accordance with ICH E6R2 guidance. A copy of the IRB approved ICF will also be provided to the subject.

10.3 Protocol and Informed Consent Changes

Changes to the protocol or Informed Consent Form will be implemented as amendments to the original document and approved by the IRB. The approvals will be processed in accordance with the established IRB procedures. Any addenda, amendment or revision that substantially alters the study design or increases potential risk to the patient requires the patient’s Consent to continue in the study.

10.4 Product Supply and Maintenance

The device will be maintained by the Sponsor, as needed. It will be supplied to the participating clinic. The device will be used according to the instructions of the Sponsor and manufacturer, InMode. At the end of

	Safety and Efficacy of Trim II for Non-invasive Lipolysis and Circumference Reduction of Abdomen.	
	Protocol No: DO609924A SIRB ID: 8659	Rev. Date: Jun 3 2022

this study, any materials provided specifically for use in this study may be returned to the Sponsor, as described in the Clinical Trial Agreement and study budget.

10.5 Privacy of Personal Data

The subject's name and personal data will remain confidential and will not be published in any way. All reports and communications relating to study subjects will identify the subject only by his/her subject number and study 2-letter code. The Study staff will complete subject identification in a confidential enrolment log, which will be used for the purposes of traceability and follow-up. This will be treated with strict adherence to professional standards of confidentiality and will be filed under adequate security and restricted accessibility.

11.1 Case Report Forms (CRFs)

Paper case report forms will be used in this trial. All protocol-required information collected during the study must be entered in the appropriate field of the case report form (CRF). The investigator, or designated representative, should complete the appropriate CRF fields as soon as possible after information is collected. The information must match the information that exists as source documents in the clinic chart, hospital chart, and/or investigator's files. An explanation should be given for all missing data.

It is the investigator's responsibility to assure the accurate completion, review, and approval of all CRFs and the timely completion and submission of all adverse event forms.

11.2 Maintenance and Retention of Records

Investigators will maintain all study related documentation for a period of five years following: 1) marketing authorization for device commercialization, or 2) sponsor's withdrawal of submission for approval, or 3) completion of the study, if the investigational device is already approved for commercialization.

Printouts provided on thermal paper should be immediately photocopied for long-term storage.

All printouts and records of tests and procedures are to be kept in a secure and safe place throughout the study. Once the study is completed, the records will be kept as required by local regulations, but in no case less than the period defined above.

	Safety and Efficacy of Trim II for Non-invasive Lipolysis and Circumference Reduction of Abdomen.	
	Protocol No: DO609924A SIRB ID: 8659	Rev. Date: Jun 3 2022

The Investigator will not relocate or dispose of any study documents before obtaining sponsor’s written permission.

Documentation should be kept so as to make its retrieval easy should an audit take place.

All study documentation will be kept locked under the Investigator’s responsibility.

11.3 Reports

Study reports include a Final Report that will be issued by the Sponsor. Report format will be designed by the Sponsor.

All study reports will be signed by the Principal Investigators approving its contents, analysis, results and conclusions.

AE related reporting requirements are specified above.

12. Monitoring Plan

12.1 General Considerations

Monitoring functions will be performed in compliance with Good Clinical Practices, EN ISO 14155, and as outlined in 21CFR§812.43(d) and 21CFR§812.46. InMode Ltd procedures detail monitoring procedures and monitor responsibilities.

The study will be monitored by the sponsor periodically at the site, per Sponsor discretion.

12.2 On-Site Visits

Periodic on-site monitoring visits are intended to assess the Investigator’s adherence to the protocol, maintenance of records and reports, and review of source documents for accuracy, completeness, and legibility, and monitoring of Adverse Events.

During periodic visits the monitor is required to:

- Assess the progress of the study towards meeting study objectives.
- Identify any concerns that stem from observations of device performance and/or review of the subject’s CRF, study management documents, and informed Consent documents.
- Monitor AE reporting and investigations.

Reports of on-site visits will be submitted by the monitor and will include, as applicable, resolution of concerns, completion of appropriate follow-up activities, completion of assigned tasks, and corrective actions. Some ‘visits’ may be performed using a video/conference call and will not be actual physical visits.

	Safety and Efficacy of Trim II for Non-invasive Lipolysis and Circumference Reduction of Abdomen.	
	Protocol No: DO609924A SIRB ID: 8659	Rev. Date: Jun 3 2022

12.3 Site Initiation Meeting

A Site Initiation visit will take place prior to initiation of study procedures. All study related documents and procedures will be explained to all staff involved in the study to ensure understanding of the study requirements. Suitability of potential study subjects will also be evaluated prior to their inclusion.

12.4 Adverse Event Reporting and Follow-up

Monitoring of adverse events, their follow up and outcomes will take place at each study visit.

12.5 Site Closure Visit

A Site Closure Visit will be conducted to ensure that all used and unused investigational devices have been returned to the Sponsor, all relevant documentation is filed and archived under the Investigator's responsibility according to regulations.

13. Risk/Benefit Analysis

13.1 Expected Risks:

As indicated in section 9.2 possible Trim II applicator adverse effects include but are not limited by:

- Pain
- Excessive redness (erythema)
- Swelling (edema)
- Muscles spasm
- Treatment area infection
- Skin burn
- Pigmentation change
- Scar

*Erythema and edema lasting not longer than 24h is typical skin reaction to the treatment.

*Skin irritation and burns beneath the electrodes have been reported with the use of powered muscle stimulators.

These risks are minimal when compared to other methods of lipolysis and circumference reduction that are being utilized (such as surgical liposuction).

13.2 Expected Benefits:

The expected benefit of using the Trim II is achieving the desired lipolysis and circumference reduction via a non-invasive technique. As previously indicated, individuals seeking body contouring are currently most likely to do so via liposuction. It is obvious that the low risk profile of the Trim II greatly benefits the individual seeking such treatments as it significantly minimizes the risks associated with the procedure.

	Safety and Efficacy of Trim II for Non-invasive Lipolysis and Circumference Reduction of Abdomen.	
	Protocol No: DO609924A SIRB ID: 8659	Rev. Date: Jun 3 2022

13.3 Conclusion:

It can therefore be claimed that the expected benefits associated with the use of the Trim II outweigh its risks.

14. Data analysis

14.1 Analysis Sets

- Safety Analysis Set

The safety analysis set will include all subjects using Embrace procedures at least a single time.

- Performance Analysis Set

Performance analysis set will consist of all subjects providing at least one post treatment performance measurement.

- Treatment of Missing Values

Only observed data will be used; i.e. missing data will not be imputed.

14.2 Statistical Analysis

[figure not shown]
Means, and standard deviations for each characteristic will be calculated. Paired sample t-test will be computed to assess changes in before treatment and follow-up scores. Statistical significance will be calculated and two-tail significance level of 0.05 will be used.

15. Data Management Plan

Case Report Forms and questionnaires will be retrieved by Monitors after source data verification and resolution of monitoring queries. Documents will be delivered to InMode Ltd onsite data management facility where forms will be logged in, and then data will be entered using a double entry method.

16. References

4. [name], [name] Neuromascular Electrical Stimulation and Strength Recovery

I N M O D E

Safety and Efficacy of Trim II for Non-invasive Lipolysis and Circumference Reduction of Abdomen.

Protocol No: DO609924A SIRB ID: 8659

Rev. Date: Jun 3 2022

of Postnatal Diastasis Recti Abdominis Muscles. Ann Rehabil Med 2017;41(3):465-474 pISSN: 2234-0645 • eISSN: 2234-0653

17. Investigator Study Acknowledgment

Investigator’s Statement:

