Endpoints	
Primary Endpoints:
 
 • Efficacy of the Trim II treatment for lipolysis and abdominal circumference reduction. Evaluation of change in abdomen circumference using tape measurements in cm at the 3 months follow-up visit comparing to baseline. Success criteria: Statistically significant reduction in abdominal circumference tape measurements at the 3 months follow-up visit compared to baseline • Safety of the Trim II treatment for lipolysis and abdominal circumference reduction. The occurrence of adverse events will be followed throughout the whole study. Observation, assessment and recording of potential reactions by the investigator. Evaluations will be done immediately after each treatment and at the follow-up visits. The frequency, severity and causality of reactions will be recorded. 
Secondary Endpoints:
 
 • Efficacy of the Trim II treatment for fat and circumference reduction in abdomen, as assessed by two blinded evaluators. Evaluation of photographs at baseline and 3 months follow-up. Success criteria: Correct identification of baseline and 3-month follow-up visit photographs in at least 70% of treated subjects by two blinded evaluators. • Change in abdominal fat thickness measured by ultrasound imaging (USI) at the 3 months follow-up visit comparing to baseline. Success criteria: statistically significant change in fat thickness measurements at the 3 months follow-up visit compared to baseline. • Evaluation of change in histological samples at 3 months follow-up visit comparing to baseline. Success Criteria: Effect on fat tissue while the dermal and epidermal layers are intact with no adverse skin events • Subject's satisfaction with study treatment at 3 months follow-up visit. Subject's satisfaction with the therapy results evaluated through the Subject Satisfaction Questionnaire (5-point scale). • Treatment comfort during the study treatment. Subjects will be asked to rate discomfort using Subject's discomfort (pain) level after each treatment evaluated using the Therapy Comfort Questionnaire
Visits	
Each subject will undergo at least 5 study visits including: screening, 3 treatments and 2 follow-up visits. Duration of each treatment visit is approximately 2 hours.
 
Visit 1: Screening, baseline and 1st treatment (can occur on th same day)

I N M O D E

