6.2 Secondary Endpoints

- Efficacy of the Trim II treatment for fat and circumference reduction in abdomen, as assessed by two blinded evaluators. Evaluation of photographs at baseline and 3 months follow-up. Success criteria: Correct identification of baseline and 3-month follow-up visit photographs in at least 70% of treated subjects by two blinded evaluators.
- Change in abdominal fat thickness measured by ultrasound imaging (USI) at the 3 months follow-up visit comparing to baseline. Success criteria: statistically significant change in fat thickness measurements at the 3 months follow-up visit compared to baseline.
- Evaluation of change in histological samples at 3 months follow-up visit comparing to baseline. Success Criteria: Effect on fat tissue with no adverse effect in dermal tissue
- Subject's satisfaction with study treatment at 3 months follow-up visit. Subject's satisfaction with the therapy results evaluated through the Subject Satisfaction Questionnaire (5-point scale) as follows: +2 = Very satisfied; +1 = Satisfied; 0 = Indifferent; -1 = Disappointed; -2 = Very disappointed.
- Therapy comfort during the study treatment. Subjects will be asked to classify skin reactions (subjective evaluation) and will rate discomfort using visual analog pain scale from 0 (no pain) to 10 (intolerable pain) immediately after each treatment session.

7. Study Population

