7.2 Subject Withdrawal and Replacement

Subjects enrolled in the study can discontinue their participation at any time for any reason without prejudice or reduction in the quality of their medical care. The investigators or sponsor can terminate a

	Safety and Efficacy of Trim II for Non-invasive Lipolysis and Circumference Reduction of Abdomen.	
	Protocol No: DO609924A SIRB ID: 8659	Rev. Date: Jun 3 2022

subject's participation in this study to protect the subject's health or if the subject fails to follow directions resulting in noncompliance to study procedures. Subjects who withdraw or are terminated from the study may be replaced to ensure that at least 70 subjects have completed the study. Subjects who fail to complete the treatment will be replaced and will not be evaluable.

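### Comfort endpoint: 7.2 and 14.1 disagree on whether subjects who stop early are counted, and 6.2 names a different scale from the rest of the protocol

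*Combined protocol and SAP*

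**What the plan says.** **Who is counted.** Section 7.2 says "Subjects who fail to complete the treatment will be replaced and will not be evaluable". Section 14.1 defines two analysis sets. For safety, "The safety analysis set will include all subjects using Embrace procedures at least a single time"; I read the product name there as meaning the Trim II treatment. For performance, "Performance analysis set will consist of all subjects providing at least one post treatment performance measurement". No text assigns comfort to either set, or says whether a comfort rating is a performance measurement. Section 14.1 also says that only observed data are used.

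**Which instrument.** In 6.2, subjects "will rate discomfort using visual analog pain scale from 0 (no pain) to 10 (intolerable pain) immediately after each treatment session". The synopsis describes the same endpoint as discomfort "level after each treatment evaluated using the Therapy Comfort Questionnaire", and 8.1 says "Subject will complete Therapy Comfort Questionnaire". Table 1 in 8.5 also names the questionnaire and refers to Appendix 5. That appendix prints five ordered categories, from Very Comfortable (+2) to Pain (-2). It contains no 0 to 10 scale.

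**How it is summarised.** The visible text of 14.2 offers "Means, and standard deviations for each characteristic will be calculated" and a paired t-test of before-treatment against follow-up scores. The schedule in Appendix 1 collects comfort only at the three treatment visits, so there is no pre-treatment rating to pair. No success criterion is given for comfort.

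**The concern.** A tolerability endpoint should tell the reader how many treated subjects found a session painful. Those most likely to answer Pain are also those most likely to stop. If the rule in 7.2 is applied to comfort, a subject who rates session 1 as Pain and withdraws is replaced by someone else and disappears from the result. The error would run in the favourable direction. If 14.1 is applied, the subject stays. The plan does not say which.

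The scale conflict adds to this. On the questionnaire a high score is good; on the 0 to 10 scale a high score is bad. The case report form and the analysis cannot follow both definitions, and a statement such as the proportion reporting pain needs a cut-off on one scale and a category on the other.

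**Working it through.** The plan states no figure for comfort, so there is nothing to reproduce. The checks below show what each rule gives. The stopper counts are assumptions, because the documents give no expected rates.

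**1. Denominator.** Inputs: 70 completers (the target in 7.2), assumed to have no Pain rating, plus s further subjects who answer Pain at session 1, stop and are replaced.

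- Under 7.2 the s subjects are not evaluable: 0/70 = 0% for any s.
- Under the 14.1 safety set the proportion is s/(70 + s), with an exact (Clopper-Pearson) 95% interval:

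| s | Under 7.2 | Under 14.1 | 95% interval |
|---|---|---|---|
| 3 | 0/70 | 3/73 = 4.1% | 0.9% to 11.5% |
| 5 | 0/70 | 5/75 = 6.7% | 2.2% to 14.9% |
| 10 | 0/70 | 10/80 = 12.5% | 6.2% to 21.8% |

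The example is deliberately one-sided: no completer answers Pain and every stopper does. It shows the direction of the effect and how its size depends on s. It is not a forecast.

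**2. Instrument.** Four places (synopsis, 8.1, Table 1, Appendix 5) agree on the questionnaire. Section 6.2 stands alone with the 0 to 10 scale, which appears nowhere else in the visible text. The weight of the text favours the questionnaire, but the case report form cannot be seen.

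**3. What mean and SD leave open.** Take N = 70 ratings in one session with mean +1.00, so the scores sum to 70. With sum of squares Q, SD = √[(Q − 70)/69]. Enumerating every set of category counts gives the number of Pain answers compatible with each SD. The last column keeps only distributions with a single peak, as some of the extremes have odd shapes.

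| Q | SD | Pain, all shapes | Pain, single-peaked |
|---|---|---|---|
| 114 | 0.80 | 0 to 3 | 0 to 2 |
| 140 | 1.01 | 0 to 5 | 0 to 3 |
| 170 | 1.20 | 0 to 8 | 1 to 5 |

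So the count is not determined, but for plausible shapes the uncertainty is a few subjects.

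**4. Three sessions.** If 5 subjects answer Pain at each session, they may be the same 5 (5/70 = 7.1%) or 15 different subjects (15/70 = 21.4%). Session tables alone therefore do not give the proportion who ever answered Pain.

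**The case against.** **14.1 governs analysis.** Section 7.2 is about reaching 70 completers, and 14.1 is where analysis sets are defined, so the natural reading is that 14.1 prevails. That is a fair reading and may be what the sponsor intends. Calling non-completers not evaluable is nevertheless a statement about analysis, and comfort is assigned to no set, so the ambiguity stands.

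**Stopping for pain may be rare.** Section 4 describes individually adjustable intensity and a patient-held pause switch. This makes a large s less likely, but it does not settle the rule.

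**Pain is covered elsewhere.** Pain is an anticipated adverse event in 9.2, events are assessed after each treatment, and 6.1 records their frequency and severity. A pain rate may be available from there. However, no visible rule links a Pain answer or a 0 to 10 score to an adverse event, and the comfort rating is the subject's own.

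**A stronger reading of 14.2.** A reader might infer that the plan has chosen a mean and SD in place of counts and would hide painful sessions. The documents do not support that. Section 14.2 is a short generic section, part of which is a figure not shown. It does not exclude counts, and the plan already needs proportions that it does not list, such as the 70% photograph criterion. A mean and SD is also a common summary for a 0 to 10 pain scale. What remains is that the number answering Pain is not specified as an output.

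**Conclusion.** The point holds as two documentary contradictions affecting one descriptive secondary endpoint, and it is minor. Whether early stoppers are counted is unresolved between 7.2 and 14.1, and following 7.2 would bias tolerability favourably. The effect is zero if nobody stops because of pain, and about 4 to 12 percentage points in the assumed examples with 3 to 10 stoppers. The scale in 6.2 conflicts with the one used in four other places. The missing category counts are a gap in specification, not a wrong analysis. It would go too far to say that painful experiences will be removed or go unreported: 14.1 may be what is applied, and adverse event recording is a second route to a pain rate. The conclusion rests on reading the product name in the safety set as Trim II and on the visible text of 14.2. Primary efficacy is unaffected.

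**What to change.** - **Instrument.** Correct 6.2 to the Appendix 5 questionnaire. If the case report form actually collects the 0 to 10 scale, say so, add it to Appendix 5, and fix a cut-off in advance.
- **Denominator.** State in 14.1 or 14.2 that comfort is summarised in all subjects treated at least once, and that 7.2 removes nobody from that summary. Correct the product name in the safety set.
- **Summary.** Report the number and percentage in each category at each session, and the number and percentage of subjects who ever answered Pain with an exact 95% interval. Mean and SD can stay as an extra.

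The cost is a few sentences and table lines, using ratings already scheduled after every treatment. No extra visits or subjects are needed. The downside for the sponsor is that the tolerability result may look less favourable.
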